The benefits of AVF over AVG are least certain in older adults, as age-related biological changes independently modulate patient outcomes.¹⁰ Nationally representative cohort studies of older adults with incident ESKD have shown similar patient survival between those whose first AV access placed or used was a fistula or a graft.^{11,12} Compared with grafts, fistulas fail more often and necessitate longer times and more subsequent procedures to aid development, exposing older patients to time-consuming procedures that may negatively affect upper extremity strength and erode their quality of life.¹³⁻¹⁶ Hitherto, the contribution of pre-operative muscle strength to AV access outcomes and the impact of AV access placement on upper extremity strength and self-sufficiency have not been evaluated. We propose a randomized pilot trial in older adults with pre-dialysis advanced chronic kidney disease (CKD) or incident ESKD using a TCVC for HD who had no prior AV access surgery and have upper extremity vasculature suitable for either fistula or graft placement. Participants will be randomized to receive an upper extremity AVF-first or AVG-first access for HD.

Objectives

The primary objective of this study is to prospectively evaluate patient and vascular access outcomes in a randomized intervention and in a patient population in whom fistula-first guidelines have been applied despite the lack of proven benefit and at the detriment of more access failures and procedures. Our hypothesis is that there is a bidirectional relationship between the type of first AV access and patient outcomes as follows: a) the graft-first strategy will confer a more effective transition from TCVC-based to AV access-based HD and will limit upper extremity functional impairment from protracted access development and subsequent access procedures, and b) preoperative muscle strength will impact AVF development.

Methods and Measures

Design

This randomized pilot trial will be parallel-arm in design (Appendix A). We plan to enroll 50 patients of age ≥ 65 years, with incident ESKD or advanced CKD expected to require HD initiation within 90 days of screening. Screening for potential participants will be performed

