4. Did not undergo AV access placement in the past
5. Medically eligible to receive AVF or AVG placement as deemed by the treating nephrologist
6. Surgically eligible to receive either an AVF or an AVG
7. HD is the intended long-term modality of treatment for ESKD
8. Planning to remain within Wake Forest provided health care for at least 12 months

Exclusion Criteria

1. Presence of an AVF or AVG
2. Previous attempt(s) for AV vascular access placement
3. Native vasculature not suitable for placement of AV access
4. Imminent transplant planned (within 6 months)
5. Anticipated life expectancy <9 months

This study targets elderly population with advanced CKD and ESKD; therefore, the clinical scenario of when an elderly individual is not able to consent for himself or herself will not be uncommon. Because the study objectives will not be met without including these subjects, this study plans to enroll elderly subjects who are not able to consent for themselves. The foreseeable risks to these subjects in this study are low as is the negative impact. For elderly with impaired mental capacity, permission for study participation will be obtained from the subject's Legally Authorized Representative (LAR).

Sample Size

This pilot trial has the principal aim of testing the feasibility of randomizing initial AV access placement to an upper extremity AVG-first (intervention) or AVF-first (comparator) strategy in patients ≥ 65 years of age. For this goal, we plan to enroll 50 participants (25 per arm).

Interventions and Interactions

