Screening for potential participants will be performed in two stages. In the first stage, all patients ≥ 65 years old who have pre-dialysis CKD or have ESKD receiving chronic HD will be screened for eligibility. Of these patients, only those who did not have a previous AV access surgery and are considered for AV placement (according to goals of care established by the patient's nephrologist) will be maintained as potential participants and advanced to the second phase of screening pending determination of surgical eligibility for placement of upper extremity AVF and AVG. Ultrasound vascular mapping of both upper extremities to assess vascular anatomy is routinely performed pre-operatively at our institution. Arterial diameter of ≥ 2 mm and vein diameter of ≥ 2.5 mm at the site of AV anastomosis indicate suitability for AVF surgical creation.⁷ To complete the eligibility criteria, patients must have proper anatomy (in either upper extremity) for placement of AVF (forearm or arm) and AVG (forearm or arm). After written informed consent is obtained, participants will be allocated with equal probability to either a graft-first (intervention) or fistula-first (comparator) strategy. Allocation to AVG or AVF will be done using randomly permuted blocks of varying sizes to maintain balance between the groups.

Demographic and medical data will be collected from all participants, using direct patient interview and electronic medical records. Following randomization, collected data is derived from standard of care and from assessments specifically conducted as part of this study.

Study-specific assessments will include muscle strength (assessed with upper arm grip-strength test in each arm using a hand-held dynamometer)¹⁷, four-meter gait speed (4MGS)
¹⁸(HealthMeasures. NIH Toolbox training manual English version.

Available at: <http://www.healthmeasures.net/images/nihtoolbox/>

[Training-Admin-Scoring_Manuals/NIH_Toolbox_Training_ManualEnglish_9-25-12.pdf](http://www.healthmeasures.net/images/nihtoolbox/Training-Admin-Scoring_Manuals/NIH_Toolbox_Training_ManualEnglish_9-25-12.pdf)

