Accessed November 16, 2018), satisfaction with the vascular access (using the short-form vascular access questionnaire [SF-VAQ])¹⁹, pain at the AV access site (using the Verbal Descriptor Scale [VDS] or the modified Abbey Pain Scale [mAPS] for people who cannot verbalise)^{20;21}, level of independence (using activities of daily living [ADL] and independent ADL [IADL] instruments)^{22;23}, and health-related quality of life (using the Kidney Disease Quality of Life instrument short form [KDQOL-SF] version 1.3. which consists of a generic core (Short Form-36 [SF-36]) and an 11-item kidney disease-specific scale).²⁴, participant's

individual study experience (study conduct, intervention outcomes, and intervention decisions) (using the Qualitative Study Interview designed by the PI and safety monitor). The assessment instruments (SF-VAQ, mAPS, ADL, IADL, KDQOL-SF) are summarized in Appendix B. The schedule of assessments is summarized in Appendix C.

Data Collection and Outcome Measure(s)

Data collection at enrollment: sociodemographic characteristics (age, sex, race, marital status, educational level, living arrangement); health behaviors (smoking and alcohol consumption [no, formerly, or yes]); ESKD etiology; date of HD commencement; and pre-dialysis care (first nephrology clinic visit and number of clinic visits prior to the first HD date); Charlson comorbidity index (CCI); medications (lipid lowering drugs, anticoagulants, antiplatelets); upper limb muscle strength assessed with grip-strength test in each arm using an isometric dynamometer; gait speed. The grip-strength test will be performed twice on each hand for each assessment and the mean of the two results will be used for statistical analyses; a cut-off point <16 kg in women and <26 kg in men will define muscle weakness. The four meter gait speed (4MGS) will be assessed on a flat, unobstructed four meter delineated course by trained research staff following a standard operating procedure.

Data regarding arterial and venous diameters on pre-operative ultrasound mapping, AV access date of placement, and location of AV anastomosis will be recorded for each participant. Results of blood work obtained on a monthly basis (per standard care) at the outpatient dialysis units. This includes measurements of dialysis adequacy, anemia management, and bone-mineral metabolism.

Vascular access outcomes.

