We will begin by examining descriptive statistics (means, standard deviations, minima, quartiles, maxima) and plots of the data (histograms and boxplots) to become familiar with the data and check for outliers. The proportion of people meeting each of the feasibility and protocol adherence endpoints with accompanying 95% confidence intervals (CI) will be calculated using skew-corrected score tests with a continuity correction. The maximum uncorrected error margin associated with the estimation of consent and surgery rates is 0.138, obtained at $p=0.5$. This suggests that CI around these estimates will be tight enough to provide meaningful guideline in the design of the larger trial. We will describe participant characteristics and evaluate reasons for protocol violations. We will calculate rates of dropout and other events, although we expect low numbers. Robust regression and non-parametric methods will be used for comparisons between randomized arms. The associations between pre-operative muscle strength (continuous or binary variable) with AV access primary outcome will be tested using logistic regression. The participants will be followed for a minimum of 12 months following index AV access placement. Participants who undergo AV access placement >90 days after randomization or who experience primary or secondary AV access failure will be analyzed as randomized in the intention-to-treat (ITT) analysis. Missing data will be handled under the missing at random (MAR) assumptions in compliance with an ITT protocol.²⁶ We will pay close attention to variables with higher rates of missingness, relative to others or display missingness patterns that deviate from the MAR assumptions since they could inform and guide the development of the larger trial. Results from the pilot analyses are likely to have high variability, but will provide valuable insight that will be considered in the design of a larger trial.

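### The plan allows grip strength in raw kilograms as a predictor of access outcome with no sex term, so a sex difference in access success could be read as a strength effect

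*Combined protocol and SAP*

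**What the plan says.** Under Objectives, part (b) of the hypothesis is that "preoperative muscle strength will impact AVF development". That is a claim about an effect, not only about prediction.

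The one analysis named for it is in the Analytical Plan: "The associations between pre-operative muscle strength (continuous or binary variable) with AV access primary outcome will be tested using logistic regression". No covariate is listed, neither form is designated as main, and the plan does not say whether the model covers both arms or the fistula arm only.

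Data Collection and Outcome Measure(s) describes the predictor. Grip is tested twice on each hand and "the mean of the two results will be used for statistical analyses"; no standardisation by sex is described. For the binary form, "a cut-off point <16 kg in women and <26 kg in men will define muscle weakness". The same section lists sex among the variables recorded at enrollment.

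Sample Size gives 50 participants, 25 per arm. Interventions and Interactions describes permuted-block allocation to graft or fistula.

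**The concern.** By the protocol's own cut-offs, a grip of 22 kg is weak in a man and not weak in a woman. The binary form respects this. The continuous form, allowed on equal terms, does not: a model in raw kilograms compares a typical man with a typical woman as if they differed only in strength.

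Anything that makes access success differ by sex would then load onto the grip coefficient. Randomisation gives no protection, because grip is a baseline characteristic and not an assigned treatment.

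A positive odds ratio from the raw model could therefore not be separated from a sex difference. The two permitted forms also differ on exactly this point, so they could disagree with nothing in the plan to say which governs. The Analytical Plan intends the pilot results to inform a larger trial, so a misattributed effect could be carried forward.

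**Working it through.** **Figures in the plan.** The cut-offs differ by 26 − 16 = 10 kg. The only precision figure, 0.138 for the consent and surgery rates, is reproduced by 1.96 × √(0.25/50) = 0.1386, truncated. It is not in dispute and does not depend on this regression.

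**Assumptions (none is in the documents).** Half the participants are women. Grip has mean 30 kg (SD 7) in men and 20 kg (SD 5) in women. Strength has no effect on success within either sex. Success in men and women is 60% vs 50%, 65% vs 45%, or 70% vs 40%.

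**How much of raw grip is sex.**
- Between-sex variance: 0.5 × 0.5 × 10² = 25.
- Average within-sex variance: (49 + 25)/2 = 37.
- Sex explains 25/(25 + 37) = 25/62 = 40% of grip variance, a correlation of √0.403 = 0.63.

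**Approximate size of the spurious odds ratio.** The slope per kg is roughly the sex difference in log-odds times cov(sex, grip)/var(grip), that is, times (0.25 × 10)/62 = 0.0403. Per 5 kg the multiplier is 0.2016.

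| Success, men vs women | Log-odds difference | × 0.2016 | OR per 5 kg | Simulated OR, large sample |
|---|---|---|---|---|
| 60% vs 50% | 0.405 | 0.082 | 1.09 | 1.09 |
| 65% vs 45% | 0.820 | 0.165 | 1.18 | 1.18 |
| 70% vs 40% | 1.253 | 0.253 | 1.29 | 1.29 |

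With sex in the model, the simulated odds ratio is 1.00 in all three rows.

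**False rejection, two-sided 5% Wald test, by simulation.**

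| Gap in success | Raw grip, n=50 | Raw grip, n=25 |
|---|---|---|
| 10 points | about 6% | about 4% |
| 20 points | about 13% | about 8% |
| 30 points | about 24% | about 11% |

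Repeat runs move these by a point or so. With sex included, rejection at n=50 is about 3% to 5%. The n=25 column is the relevant one if the model is confined to the fistula arm, the group that hypothesis (b) concerns. There the test rejects less often because it has less power, but the odds ratio is just as biased.

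**Second set of assumptions, n=50.** Here 25 men and 25 women have a common within-sex SD of 5 to 7 kg, and 40% of each sex fall below the stated cut-off.
- Raw grip: false rejection of 4.1% to 4.6% if success does not differ by sex, 10.6% to 16.4% at 70% vs 50%, and 23.6% to 30.4% at 75% vs 45%.
- Raw grip plus sex: 4.1% to 4.9% throughout.
- Sex-specific binary weakness, no sex term: 4.2% to 4.9%, median odds ratio 1.00 to 1.02.
- The same binary variable when weakness is 60% in one sex and 40% in the other (success 75% vs 45%, SD 6): 6.0% to 6.8%, median odds ratio 0.76 or 1.33 depending on which sex is weaker.

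**Cost of adding sex.** The variance-inflation approximation for the standard error is 1/√(1 − 0.403) = 1.29. In simulation under the first set of assumptions, the standard error of the grip coefficient rose by about 33% at n=50 and 37% at n=25.

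**The case against.** A reader might infer that both permitted forms are confounded by sex. The documents do not support that. The only binary strength variable they define uses separate cut-offs for women and men, which handles most of the problem. Some residual bias remains if weakness is more common in one sex, but it hardly moves the false-rejection rate at this sample size.

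A reader might also infer that the plan excludes sex from the model. It does not; it names no covariates at all. That leaves the covariate unspecified rather than ruled out. The point still stands, because a model fitted as the sentence reads has grip alone.

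The strongest objection is that the harm needs access success to differ by sex, and no section says that it does. With no difference there is no bias, and with a 10-point gap false rejection stays close to nominal. Vessel size is one possible route to a difference, but the eligibility rules partly limit it: an artery of at least 2 mm and a vein of at least 2.5 mm indicate fistula suitability, and the anatomy must suit both access types. This narrows the route without closing it. The objection limits how large a problem can be claimed. It does not make the unadjusted continuous model a sound test of hypothesis (b).

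Finally, the trial is a feasibility pilot, and the plan itself warns of high variability in the results. That stands, and it sets the weight of the point.

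**Conclusion.** The concern holds for the continuous form only. Raw grip without sex gives a sex-confounded odds ratio whenever access success differs by sex: about 1.1, 1.2 and 1.3 per 5 kg for assumed gaps of 10, 20 and 30 points.

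It would be tempting to quote the 24% false-rejection rate as the size of the problem. That figure needs a 30-point gap and all 50 participants in the model; in the fistula arm alone it is about 11%. All these sizes rest on assumed grip distributions, success rates and sex split.

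The point is minor. The regression is exploratory, and the feasibility endpoints, the sample size of 50 and the comparison between randomised arms do not depend on it.

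**What to change.** In the Analytical Plan, state three things:

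1. Any model with continuous grip includes sex as a covariate, or uses grip standardised by sex.
2. The binary variable is the sex-specific weakness definition given in Data Collection and Outcome Measure(s).
3. Which of the two forms is the main analysis, with the other reported as supporting.

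Either form can lead. The weakness category needs no covariate to be largely protected; continuous grip needs the sex term.

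This takes a sentence or two and no new data, since sex is already collected. The statistical cost for the continuous form is one degree of freedom and, under the assumptions above, a standard error about one third larger for the grip coefficient. In a sample of 25 to 50 that is a real loss of precision, but the narrower interval from the unadjusted model is centred on the wrong value when success differs by sex.

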Recruitment will be determined as the proportion of people meeting inclusion criteria who ultimately consent to randomization. We aim to consent $\geq 70\%$ of those eligible. Protocol adherence is based on the ability to undergo a graft or fistula surgery within 90 days of randomization, which we aim to attain in $\geq 70\%$ of participants. Outcomes of quality of life stratified by the type of first AV-access strategy. Changes in grip strength, pain related to the access (acute and chronic pain), patient's satisfaction with the access, changes in the level of independence (ADLs and IADLs) and HRQoL—will be compared between the two arms, with baseline (preoperative) assessments used as reference.

Subject Recruitment Methods

Clinical records of Wake Forest Nephrology practice, including WFOPD facilities, WFBMC nephrology outpatient clinics, and WFBMC nephrology inpatient service will be reviewed for eligibility. Study participants will be older adults of age ≥ 65 years with a diagnosis of incident ESKD or have advanced CKD expected to require HD initiation within 90 days of screening who meet the following additional inclusion criteria: (1) use a TCVC for HD, (2) did not undergo surgical creation of an AV access in the past, (3) are medically eligible to undergo surgery for AV access placement, and (4) are surgically eligible to undergo surgical placement of AVF and AVG. Medical eligibility for surgical placement of AV access will be determined as part of standard of care for patients with ESKD. In clinical practice, this aspect takes in consideration patient's clinical prognosis (e.g., unlikely to recover kidney function, medically stable to undergo surgical placement of AV access, anticipated life expectancy ≥ 9 months) and goals of care (HD is the intended long-term modality of treatment). Surgical suitability for placement of AV access, AVF and AVG, will be determined as part of standard of care by the vascular surgeon. To make this determination, the vascular surgeon will use the results of the ultrasound vascular mapping of both upper extremities. Patients who meet all the eligibility criteria will be approached by the vascular access coordinator, study coordinator, and/or PI for explanation of study participation.

Human Subjects Protection

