Appendix D. Vascular access outcomes

Vascular access outcomes (according to the recommendations of the Committee on Reporting Standards for Arteriovenous Accesses, Society for Vascular Surgery and American Association for Vascular Surgery)	
AV access outcome	Definition
Primary access failure	Permanent failure of the fistula or graft before hemodialysis suitability. This includes inadequate maturation, thrombosis, failure of first and subsequent cannulations, and other complications leading to nonfunctional fistula or graft.
Successful cannulation	The arteriovenous access became the primary vascular access for hemodialysis (the fistula or graft access has been cannulated with two 16- or 15-gauge needles for ≥ 3 consecutive dialysis sessions and the TCVC was removed).
Suitability for hemodialysis	Fistula or graft use with two needles and maintenance of blood flow $\geq 300\text{ml}/\text{min}$ for $\geq 75\%$ of dialysis sessions over a continuous 4-week. The maturation criteria can be satisfied at any time within 6 months of fistula or graft creation surgery.
Unassisted access maturation	Criteria for fistula or graft suitable for hemodialysis (based on the above criteria) are met before any endovascular or secondary surgical procedure to facilitate maturation.
Assisted access maturation	Satisfaction of the criteria for fistula or graft suitability for hemodialysis after a procedure to facilitate maturation (e.g., angioplasty, stent placement, surgical revision, ligation of accessory veins).
Primary access patency	Intervention-free access survival defined as the time from fistula or graft creation to any intervention to maintain patency.
Secondary access failure	Permanent failure after the fistula or graft met dialysis suitability criteria with subsequent abandonment.
Noninfectious complications	Stenosis, thrombosis, hand ischemia, aneurysm, pseudoaneurysm, infiltration.
Infectious complications	Fistula or graft cellulitis, abscess, bacteremia.
Access procedures	Angioplasty, stent placement, surgical revision, ligation of accessory veins, superficialization of vein.
Other clinical outcomes	TCVC placement, new AV access surgical creation, AV access-related hospitalization or death.
Limb ischemia following AV access placement	
Symptoms	Paresthesia, pain, hand stiffness, ulceration and tissue loss in the limb with arteriovenous access.

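### Muscle strength is tested by logistic regression with no small-sample method in about 25 fistula participants (50 if arms are pooled); a Firth fit is a cheap improvement

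*Combined protocol and SAP*

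**What the plan says.** The relevant sentence in the Analytical Plan is "The associations between pre-operative muscle strength (continuous or binary variable) with AV access primary outcome will be tested using logistic regression". It is unqualified. No estimator, covariate or handling of zero cells is given, and the robust and non-parametric methods named just before it are reserved for comparing the randomized arms.

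The analysis serves hypothesis (b) in Objectives: "preoperative muscle strength will impact AVF development". Under Sample Size the trial enrolls 50, 25 per arm. Under Interventions and Interactions, "participants will be allocated with equal probability to either a graft-first (intervention) or fistula-first (comparator) strategy". The binary predictor is defined under Data Collection and Outcome Measure(s): "a cut-off point <16 kg in women and <26 kg in men will define muscle weakness".

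The plan does not identify which endpoint is the AV access primary outcome. One binary candidate in Appendix D is primary access failure: "Permanent failure of the fistula or graft before hemodialysis suitability". Nor does it say whether the model uses the fistula arm alone or both arms. The documents give no expected weakness prevalence, outcome frequency or effect size for this analysis.

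**The concern.** Read without qualification, logistic regression means maximum likelihood. In a sample of about 25 this has two known weaknesses. When the true odds ratio differs from 1, the slope estimate for a continuous predictor is biased away from the null. When any cell of the weakness-by-outcome table is empty, the odds ratio estimate is zero or infinite and the Wald interval is useless.

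The plan warns of high variability, but that concedes imprecision. It does not cover a systematic shift or an estimate that does not exist. What is at stake is the quality of the pilot's evidence on one of its two stated hypotheses. If an empty cell occurs with no rule in place, the remedy is also chosen after the data have been seen.

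**Working it through.** **The plan's own figure.** The only precision figure is a maximum error margin of 0.138 for consent and surgery rates. With n=50 and p=0.5, 1.96 × √(0.25/50) = 0.1386, so it reproduces apart from truncation. It concerns the feasibility proportions and says nothing about this regression.

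**Sample sizes.** 50 with both arms and 25 in the fistula arm. The adherence target is surgery within 90 days in at least 70%. If uptake only just meets it and only operated participants are used, 0.70 × 25 = 17.5, about 18.

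**Assumed inputs** (not in the documents): outcome frequency 20–40% except where stated; weakness prevalence 20–60%; odds ratio 3 for weakness; odds ratio 2 per SD of grip.

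**Continuous grip.** Trials were simulated with one standard-normal predictor and fitted by maximum likelihood (ML) and by Firth. With 3,000 trials per setting, the odds ratios (exponentiated mean log OR, and ML median) were:

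| n | Outcome | True OR | ML mean | ML median | Firth mean |
|---|---|---|---|---|---|
| 25 | 30% | 2 | 2.45 | 2.14 | 2.06 |
| 25 | 50% | 2 | 2.33 | 2.14 | 2.04 |
| 50 | 30% | 2 | 2.12 | 2.06 | 1.99 |
| 50 | 50% | 2 | 2.13 | 2.06 | 2.01 |
| 25 | 30% | 1 | 0.99 | 0.98 | 0.99 |

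On the log scale at n=25, ln 2.45 / ln 2 = 0.896/0.693 = 1.29 and ln 2.33 / ln 2 = 0.846/0.693 = 1.22, so the mean is 22–29% too high. The median gives ln 2.14 / ln 2 = 0.761/0.693 = 1.10, or 10% too high. At n=50, ln 2.13 / ln 2 = 0.756/0.693 = 1.09, or 9%.

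The n=25 mean depends on a long right tail, so repeated simulations range from 17% to 32%, with 20–25% a fair central figure. For outcome 20–40%, one set gave +21 to +23% at n=25 and +9 to +12% at n=50, against about 3% or less for Firth. Root-mean-square error at n=25 was 0.67–0.86 for ML and 0.54–0.66 for Firth.

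**Binary weakness.** Let w be the weakness prevalence and p₀, p₁ the outcome risks in the not-weak and weak groups. These solve (1−w)p₀ + w·p₁ = outcome frequency, with p₁/(1−p₁) = 3·p₀/(1−p₀). The four cell probabilities q follow, and the chance of an empty cell is Σ(1−q)ⁿ less small overlap terms.

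Example: w=40%, outcome 30%.
- p₀ = 0.207 and p₁ = 0.439 (check: 0.6×0.207 + 0.4×0.439 = 0.300).
- Cells: 0.176, 0.224, 0.124, 0.476.
- At n=25: 0.824²⁵ + 0.776²⁵ + 0.876²⁵ ≈ 0.008 + 0.002 + 0.036 = 0.046.

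Same calculation over the grid (chance of no finite estimate, odds ratio 3):

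| Weakness prevalence | n=25, outcome 20 / 30 / 40% | n=50, outcome 20 / 30 / 40% |
|---|---|---|
| 20% | 21 / 14 / 17% | 3 / 1 / 2% |
| 40% | 17 / 5 / 2% | 2 / <1 / <1% |
| 60% | 35 / 17 / 7% | 11 / 3 / 1% |

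The worst cell is not-weak with the outcome at prevalence 60%, outcome 20%: q = 0.4 × 0.106 = 0.0424. Then 0.9576²⁵ ≈ 0.338 at n=25. Adding 0.014 for the weak-with-outcome cell and removing the overlap gives 0.348. At n=50 the total is 0.1145. At n=18 and prevalence 40%, the figures are about 31%, 13% and 7%.

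**Direction of finite binary estimates.** At n=25, prevalence 30%, outcome 30–40% and true odds ratio 2–5, they are mostly 4–9% too high. At prevalence 70%, outcome 30% and true odds ratio 3, the average is 2.08, which is too low, because the most extreme tables are those with no finite estimate.

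**The case against.** The principal aim is feasibility of randomization, and the plan presents these results as variable insight for a later trial. The average bias for continuous grip is only about 0.2 of the estimator's own SD (0.65–0.91 at n=25), and Wald coverage among fitted trials was 97–98%, so those intervals do not mislead. The Analytical Plan does not restrict the model to fistulas. With both arms, n is 50 and both problems are smaller. A non-finite odds ratio is obvious in the output. Every size above rests on assumed inputs. Firth has its own cost: its median is about 4–7% low on the log odds ratio at n=25, and in very sparse tables it shrinks further (true odds ratio 3 gives 2.27 at n=25, prevalence 70%, outcome 20%).

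All of this stands, and it limits the point without removing it. No small-sample method is named, the hypothesis concerns fistulas, and Firth has the lower root-mean-square error at n=25. An infinite estimate will be noticed, but the plan gives no agreed response to it.

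Two stronger readings are tempting. A reader might infer that the planned analysis inflates the odds ratio whatever the truth. It does not: there is no meaningful bias at an odds ratio of 1, and for binary weakness the error can go either way. A reader might also infer that an inflated strength effect will mis-size the larger trial. The plan says only that pilot results will be considered in its design; nothing says this odds ratio will set its sample size.

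**Conclusion.** The concern holds in conditional form. If a true association exists, maximum likelihood overstates the mean log odds ratio for continuous grip by roughly 20–25% at n=25 and 10% at n=50 (median about 10% and 3–7%). For binary weakness the main issue is non-existence of the estimate: about 2–35% of trials at n=25 and 0–12% at n=50.

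These figures rest on the assumed odds ratios, prevalence and outcome frequencies. The n=25 figures also assume a fistula-only analysis, which hypothesis (b) suggests but the Analytical Plan does not state. The feasibility aim is unaffected. This is a cheap improvement to an exploratory analysis and does not threaten the trial.

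**What to change.** In the Analytical Plan, replace 'logistic regression' in the muscle-strength sentence with 'Firth penalized logistic regression with profile penalized-likelihood 95% CI'. Make continuous grip strength the main predictor and the binary weakness version supportive, and label the result exploratory.

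In the same edit, name the outcome and say whether the fistula arm alone or both arms are used. The change of estimator does not close that gap, and the size of the problem cannot be fixed until it is closed.

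The cost is a short edit with no new data or participants. The statistical price is the slightly low median at n=25 and the shrinkage toward 1 in very sparse tables, which the report should mention.

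### The only adherence benchmark pools both arms and accepts either access type, so on its own it does not show that each randomized strategy can be delivered

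*Combined protocol and SAP*

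**What the plan says.** The Sample Size section gives the pilot the "principal aim of testing the feasibility of randomizing initial AV access placement" to one of two strategies, with 50 participants, 25 per arm. Under Interventions and Interactions, "participants will be allocated with equal probability to either a graft-first (intervention) or fistula-first (comparator) strategy".

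The Analytical Plan defines the adherence endpoint: "Protocol adherence is based on the ability to undergo a graft or fistula surgery within 90 days of randomization". The target follows in the same sentence: "surgery within 90 days of randomization, which we aim to attain in $\geq 70\%$ of participants". No target, denominator or interval for adherence is given by arm.

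On precision, the Analytical Plan states: "The maximum uncorrected error margin associated with the estimation of consent and surgery rates is 0.138, obtained at $p=0.5". For the feasibility and adherence proportions, "accompanying 95% confidence intervals (CI) will be calculated using skew-corrected score tests with a continuity correction".

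The same section promises robust and non-parametric comparisons between arms in general terms, and a review of the reasons for protocol violations. The outcomes it names for comparison between arms are grip strength, access pain, satisfaction, independence and quality of life; adherence is not among them. Appendix E lists dropouts and their causes as the protocol violations and does not list receipt of the other access type.

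**The concern.** Randomizing between two surgical strategies is feasible only if patients in each arm go on to receive the strategy they were assigned. A single proportion over both arms averages this away: a well-delivered arm can carry a poorly delivered one past 70%.

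The wording of the endpoint adds a second gap. It asks for a graft or a fistula and does not say that it must be the one assigned, so crossover is not separated from adherence. Nor is crossover among the protocol violations in Appendix E, so neither measure is sure to capture it.

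At stake is what the larger trial can learn. Its design would need the rate at which each assigned strategy is delivered in time. Crossover and missed surgery can dilute a comparison by assignment, and the pooled figure does not say how much of either occurred in each arm.

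**Working it through.** **Inputs.** N = 50, 25 per arm, allocation 1:1 (Sample Size; Interventions and Interactions). Adherence aim at least 70% of participants, and stated maximum margin 0.138 at p = 0.5 with 95% intervals (Analytical Plan).

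**Step 1: reproduce the stated margin.** The uncorrected half-width is 1.96 × sqrt(p(1 − p)/n).
- n = 50, p = 0.5: 1.96 × sqrt(0.25/50) = 0.1386. This is the plan's 0.138, truncated.
- n = 25, p = 0.5: 1.96 × sqrt(0.25/25) = 0.196.
- n = 50 with a continuity correction: 0.1386 + 1/(2 × 50) = 0.149.

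Only the first matches, so the stated precision is for both arms together.

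**Step 2: what meets the aim.** 0.70 × 50 = 35 participants. Splits that give exactly 35, with the Wilson 95% CI for the weaker arm:

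| Stronger arm | Weaker arm | Weaker arm rate (95% CI) |
|---|---|---|
| 25/25 | 10/25 | 40% (23% to 59%) |
| 24/25 | 11/25 | 44% (27% to 63%) |
| 23/25 | 12/25 | 48% (30% to 67%) |

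In all three the pooled aim is met while the weaker arm's upper limit is below 70%. If only the assigned access is counted, 10/25 is the lowest the weaker arm can be, because the other arm cannot exceed 25.

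**Step 3: the literal definition.** If either access type counts, an arm can show 25/25 adherent with none of its participants receiving the assigned access. Splitting by arm without changing the definition would not reveal this.

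**Step 4: illustration under assumed true rates.** The documents give no adherence rates by arm, so every rate here is an assumption. Exact binomial sums, 25 per arm:

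| True rates | P(at least 35/50 pooled) | P(at least 18/25 in each arm) |
|---|---|---|
| 90% / 50% | 0.57 | 0.02 |
| 90% / 55% | 0.73 | 0.06 |
| 90% / 60% | 0.85 | 0.15 |
| 80% / 70% | 0.84 | 0.46 |
| 70% / 70% | 0.57 | 0.26 |
| 75% / 75% | 0.84 | 0.53 |
| 80% / 80% | 0.97 | 0.79 |
| 85% / 85% | 0.998 | 0.95 |

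The first three rows show that the pooled aim is often met despite a large gap. The next four show the price of a hard per-arm threshold. Because 17/25 is 68%, the smallest passing count is 18/25 = 72%, and it is required twice. At 80%/70% both arms truly reach 70%, yet that rule fails more often than it passes.

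**Step 5: precision of by-arm reporting.** The maximum margin is 0.196 per arm. For the difference between arms it is 1.96 × sqrt(0.25/25 + 0.25/25) = 0.277.

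**The case against.** The strongest reply is that nothing turns mechanically on the 70%. A reader might infer that the pilot can declare randomization feasible on a false basis. The documents do not support that: the figure is worded as an aim, no progression criterion is written, and the Analytical Plan itself expects high variability and says the results will be considered in designing a larger trial. This stands, and it limits the point to what is prespecified.

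A second reply is that an uneven split would be visible anyway. The date of access placement is recorded for each participant, between-arm comparisons are promised in general, and 24/25 against 11/25 could hardly be overlooked in a trial of 50 (Fisher p about 0.0001). That is fair for an extreme split. But adherence by arm is not prespecified, and moderate gaps or crossovers could go unreported.

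Third, the design works against a large gap. Participants must be surgically eligible for both accesses, already need one, and are told about both types and the random assignment before consenting. This makes a large gap less likely without ruling it out. A claim that uneven adherence is the usual way such trials fail has no support in the documents. Nor does uneven adherence by itself bias an intention-to-treat estimate of the effect of assignment when follow-up is complete; dilution is the defensible worry.

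Fourth, the phrase covering a graft or fistula may simply be shorthand for whichever was assigned. That is possible, but the text does not say so.

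Finally, a reader might conclude that each arm must reach 18/25. The table above shows why that is a debatable trade-off with 25 per arm, and it is not recommended here.

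**Conclusion.** The point holds as a gap in the endpoint's definition and reporting. The adherence benchmark is pooled by its wording, and the 0.138 margin confirms it (0.1386 at n = 50, 0.196 at n = 25). It can be met with one arm at 40% to 48% observed adherence, and read literally it does not distinguish the assigned access from the other one. It therefore does not by itself answer the principal aim.

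These conclusions rest only on the documents' sample size, target and wording. The pass probabilities rest on assumed rates and are illustrative; they do not predict what the pilot will find. The improvement is worth making because it is cheap and bears directly on the principal aim, but the plan is not invalid without it.

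**What to change.** In the Analytical Plan, change the adherence endpoint as follows:

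- Count a participant as adherent if the **assigned** access type is placed within the existing 90-day window, and report receipt of the other type separately.
- Report adherence by arm with 95% CIs, using the interval method already planned, plus the between-arm difference with its CI.
- State the per-arm maximum uncorrected margin of about 0.20 (n = 25) next to the pooled margin.
- Keep the pooled rate alongside, and say that the 70% aim will be judged in light of both arms' estimates, without a mandatory 18/25-in-each-arm pass/fail rule.

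The cost is a few sentences. No new data are needed: the randomized arm is known, and the index access and its placement date are already recorded. The downside is wider intervals, with a maximum margin of 0.196 per arm against 0.139 pooled, and about 0.28 for the difference, so only large differences between arms will be estimated clearly.
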